Speech Performance of Rugby Players when Using Different Types of Mouthguard

Research Protocol

May 18, 2018

Table of content

1. Introduction	2
2. Problem Statement	4
3. Research Questions	4
4. Hypothesis	4
5. Aim and Objectives	5
6. Methodology	6
7. References	9
8. Flow Chart of Methodology	11

1. Introduction

Participation in sports carries a considerable risk for dental injuries (Sane, 1998). The prevalence and severity of sport related dental injuries varied, with an estimate between 0.2% and 33.5%, but is likely to be underreported (Cohenca et al., 2007). The risk of injuries increased with the age of the players, especially among those involved in long hours of training and compete professionally (Turberville et al., 2003). Dental trauma often involves injuries to the tooth structure, periodontal tissue, oral mucosa and temporomandibular joints (Feliciano, 2006). The vulnerable site is upper jaw, particularly upper incisors (Glendor, 2008). These injuries often affect the appearance of the casualties, causing undue psychological stress (Berger, 2009). Furthermore restoring the injured teeth often requires extensive dental procedure with long-term follow-up at a high cost (Glendor, 2001). Thus, preventing the occurrence of dental trauma is crucial.

Mouthguards are typically composed of a thermoplastic copolymer, designed to fit over the occlusal surfaces of the maxillary teeth and extending near to the vestibular reflection (Patrick et al., 2005). Several authors demonstrated that wearing a mouthguard during sport can reduce the occurrence and severity of dental trauma (Yesil et al., 2009). Therefore, some sports authorities mandate the use of mouthguard (Quarrie et al., 2005). The purpose of using a mouthguard is to act as a buffer from trauma and provide a degree of protection for both the mouth's soft tissues (lips, gums, tongue) and hard tissues (teeth and alveolar bone) as well as protection from brain injuries (Knapik et al., 2007). The ability to protect the mouth is highly dependent on the ability of the mouthguard in shock absorption and impact dissipation (Craig et al., 2002).

There are basically three types of mouthguards that are available in the market. Type I (stock) are sold to the public and are used without any modification. Type II ('boil and bite')

mouthguards are the most commonly used mouthguards on the market and represent 90% of all mouthguards worn (Padilla et al., 1996). These are made of a thermoplastic material that is softened and then moulded to the dental arch by the user. Type III (custom-made) are made by a dentist using a mould of the patient's dental arches (Barbic et al., 2005).

However, the compliance of mouthguard use is often low. Among Malaysian university rugby players, those who discontinued using mouthguard complaint that general discomfort and speech disturbance are the main barriers to the compliance (Liew et al., 2014). The nuisance may be due to their use of poorly-fitted stock or boil-and-bite mouthguards (Liew et al., 2014). In comparison, custom-fitted mouthguards were considered the best choice because of its ability to maintaining oral moistness and adaptation, hence causing less interference with respiration and speech, while improving comfort and limiting nauseating effect (Duarte-Pereira et al., 2008). However, limited availability and higher prices hinder its widespread use (Guevara et al., 2001).

To date, the intensity and duration of oral discomfort caused by mouthguard remains unclear, with no published study to evaluate speech performance that employed acoustic analysis and sonography. Hence, the aim of this research is to evaluate the impact of wearing mouthguards on the speech performance of the athletes.

2. Problem Statement

Participation in sports expose players to increased risk of dental trauma. Thus, the purpose of wearing a mouthguard is to act as a buffer from trauma and provide a degree of protection for both the mouth's soft tissues (lips, gums, tongue) and hard tissues (teeth and alveolar bone). However, general discomfort and speech disturbance are the main barriers to the compliance of mouthguard use. The nuisance may be due to the use of poorly-fitted boil-and-bite mouthguards. In comparison, custom-fitted mouthguards were often considered the best choice because of its ability to maintaining oral moistness and adaptation, hence causing less interference with respiration and speech, while improving comfort and limiting nauseating effect. Nevertheless, the intensity and duration of oral discomfort caused by mouthguard remains unclear, with no published study to compare speech performance when using different types of mouthguard.

Therefore, this project is intended to compare the impact of different types of mouthguard on the speech performance of the athletes.

3. Research Questions

Is there any difference in speech performance when using 'boil and bite' and custom-fitted mouthguards?

4. Hypothesis

There is no difference in speech performance when using 'boil and bite' and custom-fitted mouthguards.

5. Aim and Objectives

Aim:

To compare the speech performance when using ‘boil and bite’ and custom-fitted mouthguards.

Objectives:

- a) To provide ‘boil and bite’ and custom-fitted mouthguards to athletes.
- b) To compare the immediate speech performance when using ‘boil and bite’ and custom-fitted mouthguards based on the auditive analysis and sonography of the mouthguard users.

6. Methodology

Selection criteria

The inclusion criteria are as follows:

- (i) adult female aged 18 years old and older;
- (ii) currently representing the nation and participating actively in rugby; and
- (iii) native speakers of Malay (national language).

The exclusion criteria are as follows:

- (i) did not play rugby within the last six months;
- (ii) edentulism;
- (iii) has used a mouthguard, orthodontic appliance or removable prosthodontics appliance within the last six months;
- (iv) known history of allergy to polymers; and
- (v) medical problems (ASA classification 3 and above).

Sample size

The sample size required is determined using G*Power software (available at: <http://www.gpower.hhu.de/>). The assumptions were an effect size of 0.25, 5% margin error, 80% power, within-subject measurements for the two types of mouthguard and control – not wearing any mouthguard. Correlation among measures was set at 0.5. This yielded a minimal sample size of 28. A drop-out rate of 10% was expected between first visit and fitting visit. Thus, the total sample size was adjusted to 32.

Interventions

Informed consent will be obtained before the commencement of the study. Interested participants must provide consent in written form. Simple questions will be asked to inquire about demographic details and the use of mouthguards and problems faced if not wearing one at the moment. Also, questions will be asked regarding existing speech impairment or disturbance.

Dental examination will be carried out to all the consented participants to identify edentulism and prosthesis in the mouth. Dental impression will be taken using alginate impression material and rigid perforated stainless steel trays. The impressions will be rinsed under running tap water before spraying with disinfectant. The impressions will be transported in sealed and labelled zip-lock bags.

The impressions will be casted within the same day using Type II dental stone. Fabrication of mouthguards will be carried out by technicians using Essix mouthguard sheets and vacuum machine, with the edges extend towards the vestibule and even thickness of 4mm. Sharp edges will be smoothened.

At the fitting session, each participant will be given a ‘boil and bite’ mouthguard and a custom-fitted mouthguard. For ‘boil and bite’ mouthguards, the participants will immerse the

acrylic sheet in a bowl of hot water and fit the softened sheet on their dental arches, following the manufacturer's instructions. The completed custom mouthguards will be fitted. Any complaint of sharp edges will be handled. The players will then be instructed on the care of the mouthguards.

Immediately after fitting, speech performance will be recorded digitally in standardized conditions in a soundproof room. The volunteers will be asked to pronounce 5 two-syllable words with different consonant: *paku, bola, dadu, tatu*. Four recordings will be done, for each of the following conditions: (i) not using mouthguard; (ii) using a 'boil and bite' mouthguard; and (iii) using a custom-fitted mouthguard. The recording samples will be digitized into a computer.

Data analysis

Demographic data will be summarized using descriptive statistics. Audio recordings will be digitized with Praat software. Mean voice onset time will be compared using repeated measure ANOVA with post hoc Tukey test. However, if normality assumption is violated, the non-parametric equivalent, Friedman's test and post hoc Wilcoxon signed-rank test will be used.

7. References:

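### The stated 80% power belongs to the three-condition omnibus test, not to the boil-and-bite versus custom comparison, which is the only hypothesis stated

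*Combined protocol and SAP*

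**What the plan says.** The hypothesis (section 4) reads "There is no difference in speech performance when using" the boil-and-bite and the custom-fitted guard. The research question (section 3) and objective (b) name the same pair, as does the aim in section 5: "To compare the speech performance when using" these two guards. No hypothesis involves the no-mouthguard condition. The Introduction is broader: "the aim of this research is to evaluate the impact of wearing mouthguards on the speech performance of the athletes".

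The Sample size paragraph (section 6) is built on three conditions: "The assumptions were an effect size of 0.25, 5% margin error, 80% power, within-subject measurements for the two types of mouthguard and control", the control being no mouthguard, with a correlation of 0.5 among measures. It continues "This yielded a minimal sample size of 28" and, after 10% dropout, "Thus, the total sample size was adjusted to 32". It does not name the effect-size metric or mention sphericity.

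The Data analysis paragraph (section 6) compares mean voice onset time by repeated-measures ANOVA with post hoc Tukey tests. If normality fails, it uses Friedman's test with post hoc Wilcoxon signed-rank tests. No comparison is called primary.

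**The concern.** A reader will take the 80% as the chance of answering the stated hypothesis. It is the chance of finding some difference among three conditions, and a difference between either guard and no mouthguard counts towards it. The overall test can therefore be significant because wearing any guard changes speech, while the comparison the study was set up to make is inconclusive. The plan gives no figure for how likely that is, and it applies a three-pair Tukey penalty to the one pair it asks about.

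**Working it through.** **Inputs.** From the Sample size paragraph: effect size 0.25, alpha 0.05, power 80%, m = 3 conditions, correlation ρ = 0.5, dropout 10%. Assumed, because not stated: 0.25 is Cohen's f, sphericity holds, variances are equal.

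**1. The plan's own figure.** Noncentral F with λ = f²·n·m/(1−ρ) and df 2 and 2(n−1). At n = 28, λ = 0.0625 × 28 × 3 / 0.5 = 10.5.

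| n | 27 | 28 | 29 | 32 |
|---|---|---|---|---|
| Omnibus power | 79.6% | 81.2% | 82.7% | 86.6% |

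So 28 is the smallest n that reaches 80%, and 28/0.9 = 31.1 rounds up to 32. Both figures reproduce. Other readings do not give 28: two conditions at f = 0.25 need 34, and a single paired difference of 0.25 SD needs 128. The 80% is therefore omnibus power.

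**2. What f = 0.25 implies for the two guards.** Over all patterns of three means, the pair difference runs from 0 (guards equal, control apart) to f·√6 = 0.612 SD (guards at the extremes, control midway).

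The Problem Statement says custom guards are considered the best choice, "hence causing less interference with respiration and speech", and adds: "The nuisance may be due to the use of poorly-fitted boil-and-bite mouthguards". That suggests an order: no mouthguard, custom, boil-and-bite. Place custom a fraction c of the way from no mouthguard to boil-and-bite, with total distance D (in SD):

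- f² = (2/9)·D²·(1 − c + c²), so D = 3f/√(2(1 − c + c²))
- pair difference d = (1 − c)·D
- c = 0: d = 0.75/√2 = 0.530
- c = 1/4: D = 0.75/√1.625 = 0.588, d = 0.75 × 0.588 = 0.441
- c = 1/2: D = 0.75/√1.5 = 0.612, d = 0.306
- c = 1: d = 0

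d falls steadily as c rises, so 0.530 is the maximum in this order.

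**3. Power for the pair.** The standardised paired difference is d/√(2(1−ρ)), which equals d at ρ = 0.5. Noncentrality is d√n; for d = 0.530 and n = 28 it is 2.81. Tukey uses df = 2(n−1) and critical value q/√2 (2.41 at n = 28). The paired t-test uses df = n−1 and two-sided 0.05.

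| Pattern | d (SD) | Tukey, 28 (32) | Paired t, 28 (32) |
|---|---|---|---|
| Guards at extremes, control midway | 0.61 | 79% (85%) | 88% (92%) |
| Custom equal to no mouthguard | 0.53 | 65% (72%) | 77% (83%) |
| Custom a quarter of the way | 0.44 | 47% (54%) | 61% (68%) |
| Even steps | 0.31 | 22% (26%) | 35% (39%) |

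The difference detectable with 80% power is 0.62 SD (28) and 0.57 SD (32) for Tukey, and 0.55 SD and 0.51 SD for the paired test.

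**4. Completers.** With 32 enrolled and 10% dropout, the expected number is 28.8. The chance of at least 28 is 79% and of at least 29 about 60%. Even in the most favourable pattern, Tukey needs 29 completers to pass 80% (81%).

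**5. Significant overall, inconclusive on the hypothesis.** In a simulation of 20,000 trials at n = 28, the omnibus test was significant while the Tukey pair was not in 17% of trials when custom equals no mouthguard, and in 59% with even steps.

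**The case against.** The plan contains no arithmetic error. Sample size and analysis match each other, the plan never says the 80% applies to the two-guard pair, and ANOVA followed by Tukey is a valid, conservative way to test it. All of that stands. The control condition is also legitimate, given the broader aim in the Introduction.

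The strongest objection is that the unfavourable figures depend on an assumed order. The background speaks of interference with speech, not of voice onset time, and does not say where the no-mouthguard mean falls. If the guards are the two extremes, Tukey power is 79% at 28 and 85% at 32. So the documents do not show that the pair is underpowered. They do show that its power is unstated and not fixed by the plan's inputs.

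Two further points stand in part:

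- The Tukey penalty applies only to the parametric branch. The Wilcoxon tests carry no stated adjustment, though they too are post hoc, after Friedman's test.
- The fix does not remove the discordance. With an unadjusted paired t-test at n = 28, a significant omnibus test with a non-significant pair still occurs in about 9% (custom equal to no mouthguard) and 47% (even steps) of simulated trials.

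It might also be said that the objectives already show which comparison matters. They do, but the test and the power statement do not follow from them.

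**Conclusion.** The concern holds. The 80% at 28 players is power for the three-condition omnibus test. The stated hypothesis is one of three post hoc pairs, is not named primary, and has no stated power or detectable difference.

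That much follows from the plan's inputs, with 0.25 read as Cohen's f under sphericity. The size of the shortfall is conditional. If custom lies between no mouthguard and boil-and-bite, Tukey power for the hypothesis is at most 65% at 28 completers and 72% at 32, and much lower if custom is well away from no mouthguard. Only with the guards near opposite extremes does it come close to the stated 80%. The point should be fixed: it does not invalidate the study, but the correction gains power at no cost in enrolment.

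**What to change.** **Analysis.** Name the within-player difference, boil-and-bite minus custom, in mean voice onset time as the single primary comparison. Test it two-sided at 0.05 and report a 95% confidence interval, whatever the omnibus result. Use a paired t-test (Wilcoxon signed-rank if normality fails) or the equivalent unadjusted ANOVA contrast. Define the mean so that each player contributes one value per condition; the power figures assume this. Make the omnibus test and the two comparisons with no mouthguard secondary, with an adjustment suited to two comparisons, such as Holm.

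**Sample size.** Keep 32. Name the effect size as Cohen's f, state the sphericity assumption, and say that the 80% refers to the omnibus test. Add that, for the primary contrast, 28 completers give 80% power for a standardised paired difference of about 0.55 (about 0.51 if all 32 complete), and about 35% at 0.31 SD with 28. Present this as what the fixed enrolment can detect, not as a justified target.

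**Cost.** Two paragraphs to reword; no extra players or recordings. The stated detectable difference is less favourable than the present text suggests, power for small differences stays low, and the comparisons with no mouthguard become secondary.

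### The text describes no masking, file coding or random reading order for measuring voice onset time, a cheaply avoidable route to bias if onsets are marked or excluded by hand

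*Combined protocol and SAP*

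**What the plan says.** Section 6 (Interventions) has each player record a set of words under three conditions: no guard, boil-and-bite guard and custom-fitted guard. It states that "speech performance will be recorded digitally in standardized conditions in a soundproof room" and that "The recording samples will be digitized into a computer". Section 6 (Data analysis) adds "Audio recordings will be digitized with Praat software" and "Mean voice onset time will be compared using repeated measure ANOVA with post hoc Tukey test", with Friedman and Wilcoxon tests if normality fails.

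That is all the text says about turning sound into data. It names no reader, onset-marking rule, file coding, reading order or rule for dropping a recording, and it does not mention masking. Objective (b) in section 5 says the comparison is "based on the auditive analysis and sonography of the mouthguard users", but section 6 does not describe the auditive part. The section 8 flowchart was not legible in the copy reviewed, so this point concerns the text only.

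**The concern.** The one safeguard stated, standardized recording in a soundproof room, governs how speech is captured. It does not govern how VOT is read from the recording. Players cannot be masked to wearing a guard, so the measurement step is the practical place to mask.

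A reader could hold an expectation. Section 2 reports that custom guards are often considered the best choice, "hence causing less interference with respiration and speech". That remark concerns speech in general, not VOT, and the formal hypothesis in section 4 is a null one ("There is no difference in speech performance when using" the two guards), so no direction of bias is established. One example would be two guards that truly shift VOT equally, with a reader who knows the condition placing custom-guard onsets a little nearer the no-guard values. The trial would then tend to find a guard difference that does not exist, on the comparison that is its stated aim. A systematic shift of this kind does not average out with more recordings or more players.

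**Working it through.** **The plan's own figure.** Inputs from section 6 (Sample size): f = 0.25, 5% error (read as alpha = 0.05), 80% power, m = 3 conditions, correlation 0.5. Sphericity is assumed.

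- Noncentrality = f² × N × m / (1 − correlation). At N = 28 this is 0.0625 × 28 × 3 / 0.5 = 10.5, on 2 and 54 df.
- Power is 0.8125 at N = 28 and 0.796 at N = 27, so the minimum of 28 reproduces.
- 28 / 0.90 = 31.1, rounded up to 32, which also reproduces.

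Masking changes none of this.

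**Illustration of a reader shift.** The documents give no VOT standard deviation, reader error or bias size, so every shift below is assumed. There is no true difference between the two guards. The shift is in units of the SD of the paired difference; at correlation 0.5 this equals the SD of a single condition, since √(2 × (1 − 0.5)) = 1.

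Tukey contrast with pooled error, df = (n − 1)(3 − 1):

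- n = 28: df = 54, q = 3.408, critical |t| = 3.408/√2 = 2.410
- n = 32: df = 62, q = 3.396, critical |t| = 3.396/√2 = 2.401

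The rejection rate is the two-sided tail of a noncentral t with noncentrality shift × √n. For example, at n = 28 and a shift of 0.2, this is 0.2 × 5.29 = 1.06.

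| Assumed shift (SD of paired difference) | n = 28 | n = 32 |
|---|---|---|
| 0 | 1.9% | 1.9% |
| 0.1 | 3.6% | 3.9% |
| 0.2 | 9.6% | 10.9% |
| 0.3 | 21.5% | 24.9% |

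The rate is below 5% with no shift because Tukey shares the error across three contrasts. It reaches 5% at a shift of 0.132 SD (n = 28) or 0.123 SD (n = 32).

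**Check in the scenario of the example.** Simulation used 200,000 runs per setting, SD 1, correlation 0.5, and means of 0 (no guard), 0.5 (boil-and-bite) and 0.5 minus the shift (custom). It gave 2.0%, 3.6%, 9.7% and 21.5% at n = 28, and 1.9%, 4.0%, 10.7% and 24.8% at n = 32. Also requiring a significant overall F hardly changes this: 2.0%, 3.6%, 9.6% and 21.4% at n = 28. With no guard effect at all, and without the F requirement, the rates at n = 28 are 1.9%, 3.7%, 9.7% and 21.8%, so the contrast does not depend on the no-guard mean.

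Nothing was computed for the Friedman/Wilcoxon fallback.

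**The case against.** The strongest reply is that the harm needs two things the documents do not establish: that onsets are marked, checked or dropped by hand, and that the person doing so knows the condition. Silence does not show either. A fixed script with fixed rules would leave little room for expectation, and the text describes no exclusion of recordings. The more basic gap is therefore how VOT is measured at all, and masking matters only once that is known.

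The figures also say little about this trial. Any bias, if large enough, raises the false-positive rate, and nothing shows that a reader timing an acoustic event would reach 0.13 SD. Sphericity and a pooled error term are assumptions of the calculation, not statements of the protocol. The expectation itself rests on a general remark about speech. Masking may also be partial, because wearing a guard may be audible and a reader who attended the sessions may recognise voices.

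Most of this stands as a limit on size: the bias is possible, not shown, and the percentages should not be read as estimates. It does not remove the gap. The protocol does not say that measurement is scripted, and a team following it as written has no barrier between the known condition and the reading of the only analysed outcome. Audibility mainly affects comparisons with no guard; the two guards may be harder to tell apart, so masking can still help the comparison that matters most.

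**Conclusion.** The concern holds, conditionally. The text describes no masking, coding or random reading order for VOT, and the soundproof room covers recording only. If onsets are marked, checked or excluded by hand with the condition known, the guard-versus-guard result is open to reader bias of unknown size and direction. A shift under about 0.12 to 0.13 SD of the paired difference would leave the Tukey contrast's false-positive rate below 5%. Shifts of 0.2 to 0.3 SD would take it to roughly 10% to 25%. These figures rest on assumed shifts, sphericity and the ANOVA/Tukey route. Fully scripted marking with fixed rules would leave much less room for the problem. The change is worth making because prevention costs very little, not because a bias has been demonstrated. Confidence is medium.

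**What to change.** In section 6 (Data analysis), first state whether onsets are marked by hand or by script. Then add text such as:

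> Audio files will be given random codes and pooled across participants and conditions in random order before VOT is measured in Praat. A team member who does not measure VOT will hold the condition key, which is merged only after all measurements and token exclusions are locked.

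Apply the same procedure to any auditive rating carried out under objective (b).

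The cost is slight file handling: renaming the files, and one team member who does not measure VOT to hold the key. Sample size, visits and participant procedures do not change. The protocol should acknowledge that masking may be only partial.

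### On the non-parametric route, the trial's one question (boil-and-bite versus custom-fitted) appears to wait behind Friedman's three-condition test, which lowers its power with no gain

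*Combined protocol and SAP*

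**What the plan says.** Research Questions, Hypothesis and Aim (sections 3 to 5) each name one contrast: boil-and-bite against custom-fitted. The no-mouthguard condition enters as a control in section 6.

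The Sample size paragraph in section 6 reads "The assumptions were an effect size of 0.25, 5% margin error, 80% power", with "within-subject measurements for the two types of mouthguard and control", and adds "Correlation among measures was set at 0.5". It concludes "This yielded a minimal sample size of 28", raised to 32 for 10% drop-out. The paragraph names no test, but these are the inputs of a repeated measures ANOVA, which Data analysis gives as the main method for mean voice onset time.

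Data analysis then provides a fallback: "However, if normality assumption is violated, the non-parametric equivalent, Friedman's test and post hoc Wilcoxon signed-rank test will be used". It gives no power for that route, no rule for judging normality, and no statement of whether the Wilcoxon tests depend on Friedman's result. The documents give no distribution for voice onset time.

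**The concern.** With three conditions, Friedman's test uses only the ranks 1, 2 and 3 within each player and ignores the size of the differences. The Wilcoxon signed-rank test of two conditions does use size. If the Wilcoxon test is reached only through a significant Friedman test, the comparison the trial exists to make has to pass a blunter test of a broader hypothesis first.

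A real difference between the guards could then be missed on a route that the plan itself foresees. A reader could also take the description of Friedman as the counterpart of ANOVA to mean that the 80% carries over to it.

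**Working it through.** **Inputs.** From Sample size: effect size 0.25 (read as Cohen's f), 5% (read as the type I error), m = 3 conditions, correlation 0.5, n = 28. Assumed, because the documents do not give them: sphericity, the error shapes, the patterns of condition means and, in step 5, the normality test.

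**1. The plan's own figure.** λ = n × m × f² / (1 − ρ) = 28 × 3 × 0.0625 / 0.5 = 10.5, with 2 and 54 df. Power is 81.2% at n = 28 and 79.6% at n = 27, so 28 reproduces. 28 / 0.9 = 31.1, which rounds up to 32.

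**2. Friedman's efficiency.** Relative to the F test under normal errors it is (3/π) × k/(k + 1) = 0.955 × 3/4 = 0.716 for k = 3. That implies 28 / 0.716 = 39.1 players. Simulation agrees: about 38-40 completers for 80%, and about 72% power at n = 32.

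**3. Omnibus power at n = 28** (20,000 simulated trials per case; three mean patterns scaled to f = 0.25; normal player effect plus the named within-player error). ANOVA stays at 81-85% throughout.

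| Within-player error | Friedman |
|---|---|
| Uniform | 62-63% |
| Normal | 66-67% |
| Logistic | 72-73% |
| Gamma(4), skew 1.0 | 74-76% |
| t, 5 df | 77-78% |
| Gamma(2), skew 1.4 | 80-83% |
| Laplace | 81-82% |
| t, 4 df | 82% |
| Exponential | 88-93% |
| t, 3 df | 91% |

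The shortfall is therefore confined to mild departures. It also depends on where the non-normality lies: if the whole outcome is non-normal, rather than only the within-player error, Friedman has about 75% for uniform and 85-87% for gamma(2).

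**4. The gate on the guard comparison** (normal within-player errors, n = 28, Wilcoxon at 5%). With total SD 1 and correlation 0.5, the SD of a paired difference is √(2 × (1 − 0.5)) = 1.

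- Equally spaced means (−1, 0, 1) have root mean square √(2/3) = 0.816. Scaled to 0.25, the step is 0.25 / 0.816 = 0.306, so the extremes differ by 0.61 SD and neighbours by 0.31 SD.
- With one condition apart (2, −1, −1), the root mean square is √2 = 1.414 and the gap is 3 × 0.25 / 1.414 = 0.53 SD.

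| Position of the control | Guard difference | Direct Wilcoxon | Only after Friedman |
|---|---|---|---|
| Midway between the guards | 0.61 SD | 0.85 | 0.65 |
| Equal to custom | 0.53 SD | 0.75 | 0.60 |
| At one end, custom midway | 0.31 SD | 0.32 | 0.28 |

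The gated comparison needs both tests to be significant, so its power can never exceed that of the direct test. The direct test of this one pre-specified pair kept its type I error at 0.04-0.05.

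**5. The whole procedure.** Suppose Shapiro-Wilk p < 0.05 sends the analysis to Friedman and ANOVA is used otherwise. Omnibus power of the two-stage procedure is about 77-89% over the shapes tried when each condition is checked. It falls to about 74-75% when skewed spread between players triggers the switch while within-player errors stay normal.

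**The case against.** The case on the other side is substantial, and most of it stands.

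- *Nothing in the documents is miscalculated.* The 28 is correct for the planned main analysis, and the plan nowhere claims 80% for the fallback. Calling Friedman the counterpart of ANOVA is common shorthand, not a statement about power.
- *The weakest figures assume conditions in which the fallback is seldom used.* With fully normal data, an assumed Shapiro-Wilk check fires in about 3% of trials on residuals and about 15% if each condition is tested. When the departure is strong, Friedman does well. The exception is skew between players with normality judged on raw values. For a gamma(2) player effect the switch occurs in 33% of trials, and in those Friedman has 67% against 82% for ANOVA. The plan does not say how normality is judged, so this case can be neither assumed nor excluded.
- *The largest gate loss rests on one mean pattern.* It requires the control to lie between the two guards, so that they shift voice onset time in opposite directions. This is why three patterns are shown; in one of them the loss is only 0.04.
- *The gate is inferred.* Data analysis writes post hoc and states no conditional rule. If the sponsor intends the Wilcoxon test to run regardless, the plan should say so, and the same sentence settles it.
- *An aligned-rank test is not a like-for-like replacement.* It treats deviations as comparable in size across players, which Friedman does not. Changing the omnibus test is a matter of preference.

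A reader might infer that the trial as planned has only 63-78% power, or that 80% is attainable with ANOVA alone. The documents support neither: that range is conditional on reaching the fallback under mild departures, and Friedman reaches 80% or more for several plausible shapes.

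**Conclusion.** The point holds in a limited form. On the fallback route, the trial's only research question appears to be tested behind a three-condition test that is weaker than ANOVA when departures from normality are mild (about 63-78% against about 81%). Under normal within-player errors the gate costs about 0.20, 0.15 or 0.04 of power for the guard comparison (0.85 − 0.65, 0.75 − 0.60, 0.32 − 0.28), depending on the position of the control. Removing it cannot lower that power, and the direct test holds its size.

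The figures rest on the conventional reading of post hoc and on assumed error shapes and mean patterns. Overall power of the two-stage procedure is roughly 74-89% under an assumed Shapiro-Wilk trigger, depending on the shape and on how normality is judged. This is a free improvement, not an error that invalidates the sample size.

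**What to change.** In Data analysis, state that if the non-parametric route is taken, boil-and-bite versus custom-fitted is tested directly by the Wilcoxon signed-rank test at 5%, whatever the result of Friedman's test. Label Friedman's test and the two comparisons with no mouthguard as secondary.

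In Sample size, add that the 80% at 28 players was calculated for repeated measures ANOVA.

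The cost is two or three sentences, with no extra players or recordings. Replacing Friedman by an aligned-rank test or a within-player permutation of the F statistic is optional, and the point does not depend on it.
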